3.1. Study Rationale

[figure not shown]
Pharmacokinetic data from the first time in human (FTIH) study for GSK2982772 (200975) [GlaxoSmithKline Document Number [2014N204126_03](#)] showed that the half-life of GSK2982772 was short (~2 to 3 hours). As a result, BID and three times daily (TID) dosing regimens are being evaluated in three ongoing proof of mechanism studies. A QD formulation would be more convenient from a patient perspective and could offer the advantage of providing a flatter GSK2982772 concentration time profile. This current study is being conducted to evaluate the feasibility of developing an MR formulation using a minitab approach filled into a capsule. Each minitab will contain 5 mg GSK2982772 and the amount of polymer can be adjusted to achieve the desired in-vitro release profile. In addition, the number of minitabs included in the capsule can be varied to adjust the dose.

The Clinical Trial Authorisation application for this study describes a flexible protocol design using the concept of formulation design space to allow decision-making in response to interim PK observations. The principles of a flexible protocol were discussed and agreed with the Medicines and Healthcare products Regulatory Agency (MHRA) at a Scientific Advice Meeting between the MHRA and Quotient Sciences (formerly Pharmaceutical Profiles).

Based upon the concept of formulation design space, specific Investigational Medicinal Products (IMPs) are not detailed within the Investigational Medicinal Product Dossier but rather a defined range of formulation inputs and corresponding performance outputs are described and justified based on in vitro studies.

There will be the option to test a range of formulations based on a 2-dimensional design space describing the dose level and release rate of the IMP ([Figure 1](#)).

Figure 1 Two-Dimensional Design Space for the Modified Release Formulation of Capsules Filled with Minitabs

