5.1. Overall Design

This is an open label, single centre, three part, single and repeat dose study in healthy male and female participants to assess MR minitab formulations of GSK2982772 in a capsule. Assuming a suitable MR minitab formulation in a capsule is identified, the impact of food (high-fat meal) on the rate and extent of absorption will be evaluated as well as an assessment of the relationship between dose and systemic exposure to GSK2982772 following repeat dosing for 3 days. MR tablet formulations of GSK2982772 will also be investigated, along with the impact of food on the rate and extent of absorption.

[figure not shown]
Part A of the study is a non-randomised 6 period, sequential, 6-way fixed sequence design in which up to 4 MR minitab formulations in a capsule may be evaluated following single dose administration in the fasted state (120 mg) (Figure 2). Periods 1, 2 and 3 will evaluate a slow MR release duration (nominally 24 hours), a fast MR release duration (nominally 10 hours), and IR tablet, respectively. Periods 4, 5 and 6 will be flexible and the dosing regimen will be dependent on the outcome of Periods 1 to 3. In Periods 4 to 6, there will be the option to optimise the MR release duration and/or to evaluate the impact of food (high-fat meal) on the selected MR minitab formulation in a capsule. There will also be the option to cancel Periods 5 and 6 if an optimal formulation is determined in Periods 1 to 2.

Participants will be admitted to the clinic in the morning of the day before dosing (i.e. Day -1) of each inpatient period. Each inpatient period will consist of 3 days and 2 nights followed by a minimum washout of 7 days between doses. A follow-up visit will occur at least 7 days after the last study treatment. Participants will receive a single oral dose of study treatment during each inpatient period.

Figure 2 Part A Study Design – Formulation Optimisation and Food Effect

[figure not shown]

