
 
Point estimates and corresponding 90% CI will be computed for the differences in the endpoint between Day 1 and Day 3 for Period 1 (120mg daily), Period 2 (240mg daily), and Period 3 (300mg daily) for GSK2982772 minitab MR dose.
 
The point and interval estimates on the log-scale will then be exponentially back transformed to give estimates of the ratios of geometric means, <math>F_{relDay}</math>, and 90% CI. See Section 10.6.4
 

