## Pharmacokinetic Blood Sample Collection Times for Part B

[figure not shown]
Time (h)	Pre-dose	Periods 1, 2 and 3												
		Days 1 and 3												
		0	2	4	6	8	10	12	14	16	18	20	22	24
Dosing a	X													
PK sampling b	X		X	X	X	X	X	X	X	X	X	X	X c	

a Subjects will be dosed on Days 1, 2 and 3; however, no PK samples will be taken post-dose on Day 2

b PK sampling schedule may be amended based upon the PK data from Part A and/or if BID dosing is selected for Part B. If BID dosing is employed the number of PK samples may be reduced i.e. some of the samples between 14 and 24 h may not be required. In addition, the 12 h sample will be taken prior to administering the second daily dose.

c Day 1 24 h post-dose sample should be taken prior to dosing on Day 2.

PK samples should take priority over other procedures scheduled at the same time point. As guidance, the preferred order of assessments is:

Electrocardiograms (ECGs) should be taken prior to vital signs when both measurements are scheduled at the same time point. Other assessments, e.g. physical examinations etc, will be performed within the required time windows. All safety assessments will be timed and performed relative to the start of dosing.

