### 10.6.4. Pharmacokinetic

#### 10.6.4.1. Non-Compartmental Analysis

The pharmacokinetic parameters will be calculated by standard non-compartmental analysis according to current working practices using WinNonlin Version 6.3 or higher.

Pharmacokinetic Endpoints
AUC(0-t)

 
Area under the concentration-time curve from time zero to the time of the last quantifiable concentration (C(t)) will be calculated using the linear trapezoidal rule for each incremental trapezoid and the log trapezoidal rule for each decremental trapezoid.
 

Pharmacokinetic Endpoints	
AUC(0-∞) (Day 1)	

 
Area under the concentration-time curve extrapolated to infinity will be calculated as:  <math display="block">AUC = AUC(0-t) + C(t) / \lambda_z</math> 
where <math>\lambda_z</math> is the terminal phase rate constant.
 
 
	
AUC(0-24) for QD dosing	
Area under the concentration-time curve from time zero to 24 h post dose will be calculated using the linear trapezoidal rule for each incremental trapezoid and the log trapezoidal rule for each decremental trapezoid.	
AUC(0-12) for BID dosing	
Area under the concentration-time curve from time zero to 12 h post dose will be calculated using the linear trapezoidal rule for each incremental trapezoid and the log trapezoidal rule for each decremental trapezoid.	
AUC(12-24) for BID dosing	
Area under the concentration-time curve from time 12 h to 24 h post dose will be calculated using the linear trapezoidal rule for each incremental trapezoid and the log trapezoidal rule for each decremental trapezoid.	
AUC%extrap	
Percentage of AUC extrapolated beyond the last measured time point	
Cmax	
Maximum observed concentration, determined directly from the concentration-time data	
C12h for BID dosing	
Observed concentration at 12 hours, determined directly from the concentration-time data	
C24h	
Observed concentration at 24 hours, determined directly from the concentration-time data	
Tmax	
Time to reach C max , determined directly from the concentration-time data.	
Tlag	
Time from dosing at which GSK2982772 was first quantifiable in a concentration vs time profile	
t1/2	
Terminal half-life	
Notes	

 
Additional parameters may be included as required
 
	

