
Relative Bioavailability (F rel )	

 
Frel will be calculated as follows:
 
	
$F_{rel} = \frac{GeoMean\{AUC \text{ or } C_{max}(\text{test})\}}{GeoMean\{AUC \text{ or } C_{max}(\text{reference})\}} \times 100$	
F rel will be calculated using AUC (0-∞) and C max . If for any reason the AUC (0-∞) is not calculable then an alternative AUC such as AUC (0-last) , AUC (0-T) or AUC over a partial area may be used. The following comparisons will be made: 
 
MR Formulation (test) vs IR Formulation (reference)
 
Fed (test) vs Fasted (reference)
 
Day 3 vs Day 1 (reference)
 
	

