## 10.11.7.2. Pharmacokinetic Tables Part B

Pharmacokinetic: Tables					
No.	Population	IDSL / TST ID / Example Shell	Title	Programming Notes	Deliverable [Priority]
PK Concentration					
3.8.	PK	PK01	Summary of Plasma GSK2982772 Pharmacokinetic Concentration-Time Data by Dose and Day: Part B		SAC
PK Derived Parameters					
3.9.	PK	PKPT1	Summary Statistics of Derived Plasma GSK2982772 Pharmacokinetic Parameters by Dose and Day: Part B	Parameters with units	SAC
3.10.	PK	PKPT3	Summary Statistics of Log-Transformed Derived Plasma GSK2982772 Pharmacokinetic Parameters by Dose and Day: Part B	Parameters with units	SAC
3.11.	PK	PKPT3	Summary Statistics of Log-Transformed Derived Plasma GSK2982772 Dose-Normalized Pharmacokinetic Parameters by Dose and Day: Part B	Parameters with units	SAC
PK Analyses					
3.12.	PK	PK_T2	Summary of Statistical Analysis of Plasma GSK2982772 PK Parameters (AUC & C) Assessing Relative Bioavailability of Repeat Dose: Part B		SAC

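### The Part B Day 3/Day 1 ratio of AUC(0-24) under once-daily dosing is an accumulation ratio, but the SAP reports it as a relative bioavailability

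*SAP*

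**What the plan says.** Part B participants receive three days of treatment in each period: "Subjects will be dosed on Days 1, 2 and 3" (SAP Appendix 2). For once-daily dosing, SAP 8.2.5.2 models log AUC(0-24) and log Cmax with dose, day and their interaction. It then states: "Point estimates and corresponding 90% CI will be computed for the differences in the endpoint between Day 1 and Day 3", for each of the three periods. The back-transformed result is named FrelDay.

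SAP 10.6.4.1 defines Frel as a ratio of geometric means and lists "Day 3 vs Day 1 (reference" beside the formulation and food comparisons. The output, Table 3.12, is titled "Assessing Relative Bioavailability of Repeat Dose: Part B", and Figure 3.13 uses the same description.

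SAP 10.6.4.1 defines AUC(0-24) as "Area under the concentration-time curve from time zero to 24 h post dose", with no adjustment for earlier doses. The general Frel rule there prefers AUC(0-inf) and falls back on another AUC, including a partial area, when AUC(0-inf) cannot be calculated. However, AUC(0-inf) is defined for Day 1 only and appears neither in the Part B parameter list (SAP 8.2.1.2) nor among the Part B model endpoints (SAP 8.2.5.2). The AUC ratio in Part B is therefore AUC(0-24) over AUC(0-24).

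**The concern.** A relative bioavailability compares how much drug is absorbed on two occasions. AUC over the same 24 h window on Day 1 and Day 3 does not do that when exposure from one dose runs past 24 h. The Day 1 window loses the tail, and the Day 3 window gains the tails of earlier doses. Identical absorption on both days then gives a ratio above 100%.

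The related Part B objective asks whether absorption changes with dose on repeat dosing (Protocol 4). A figure above 100% under a relative bioavailability title could be taken to mean that absorption rose. SAP 5.1 also shows Periods 1 and 2 fasted and Period 3 fed. If food altered the length of the tail, FrelDay could differ between periods with bioavailability unchanged. Neither document calls the ratio accumulation or corrects for carry-over.

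**Working it through.** The documents state no expected Day 3/Day 1 ratio, so there is no figure to reproduce. The check asks what the ratio would read if bioavailability were the same on both days.

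**Inputs from the documents**
- Doses on Days 1, 2 and 3 (SAP Appendix 2), 24 h apart under once-daily dosing.
- Half-life, Protocol 3.1: "half-life of GSK2982772 was short (~2 to 3 hours".
- Release duration of the slow minitab, Protocol 5.1: "Periods 1, 2 and 3 will evaluate a slow MR release duration (nominally 24 hours". SAP 5.1 labels this formulation, and every Part B arm, MT-12h without defining the label.

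**Assumptions not in the documents**
- One compartment, linear and time-invariant kinetics.
- Release either zero-order or first-order.

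**Formula.** By superposition, Day 3 AUC(0-24) is the single-dose AUC over 0-24, 24-48 and 48-72 h added together, so

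R = single-dose AUC(0-72) / single-dose AUC(0-24).

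When almost nothing remains after 72 h, R = 1/(1 − f), where f is the fraction of single-dose AUC falling after 24 h. This relation does not depend on the release shape; only f does.

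**Zero-order release over D hours (D ≤ 24), k = ln 2 / half-life:** f = [exp(−k(24 − D)) − exp(−24k)] / (kD).

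- D = 24, half-life 2 h: 24k = 8.318; f = (1 − 1/4096)/8.318 = 0.120; R = 1/0.880 = 1.137.
- D = 24, half-life 3 h: 24k = 5.545; f = (1 − 1/256)/5.545 = 0.180; R = 1/0.820 = 1.219.
- D = 12, half-life 2 h: f = (1/64 − 1/4096)/4.159 = 0.0037; R = 1.004.
- D = 12, half-life 3 h: f = (1/16 − 1/256)/2.773 = 0.0211; R = 1.022.

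**First-order release with rate ka:** the fraction of AUC collected by time T is 1 − [k·exp(−ka·T) − ka·exp(−kT)]/(k − ka). For 80% released by 24 h, ka = −ln(0.2)/24 = 0.0671. At a half-life of 2 h the fractions are 0.752 at 24 h and 0.990 at 72 h, so R = 0.990/0.752 = 1.316.

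| Assumed release | Half-life 2 h | Half-life 3 h |
|---|---|---|
| Zero-order over 12 h | 100.4% | 102.2% |
| Zero-order over 20 h | 103.7% | 109.3% |
| Zero-order over 24 h | 113.7% | 121.9% |
| First-order, 80% out by 12 h | 107.0% | 109.9% |
| First-order, 90% out by 24 h | 115.9% | 120.0% |
| First-order, 80% out by 24 h | 131.6% | 137.4% |

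**Cmax.** The Day 3/Day 1 ratio is at most 1.004 in the zero-order cases and runs from 1.07 to 1.35 in the first-order cases shown.

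**Would AUC(0-inf) on both days avoid the problem?** No. After the Day 3 dose it would still include the Day 2 tail. For 24 h zero-order release the ratio would be about 1 + f, or 112 to 118%.

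**Can Day 1 AUC(0-inf) be estimated?** Part B sampling for each profile stops at 24 h. With zero-order release over 24 h, concentration is proportional to 1 − exp(−kt) up to the last sample. It has not begun to fall, so there is no terminal slope to fit. In the first-order case with 80% out by 24 h, 25 to 28% of AUC would have to be extrapolated (1 − 0.752 and 1 − 0.720).

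**The case against.** The strongest reply is that little turns on the label. No objective in either document asks about Day 3 against Day 1. No hypothesis is tested, Part B has no interim analysis, and no decision rule uses FrelDay. Dose-dependent absorption is addressed by dose-normalised summaries and plots (Protocol 10.4.1, SAP 8.2.2). The day contrast is openly identified, so a careful reader can see what was divided by what. If MT-12h means that release is complete by 12 h, the distortion is about 0.4 to 2%.

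All of that stands, and it limits the size and consequence of the point. It does not make the label correct.

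A reader might infer three stronger things that the documents do not support:
- **That the ratio is inflated by about 20%, or by no more than that.** The 24 h duration is a nominal release time, not an in vivo absorption time. The SAP's own label points to a much smaller effect, and slower first-order release would give a larger one.
- **That this is the only modelled result in Part B.** That is true of the SAP's Part B tables, but Protocol 10.4.1 also plans to model the standard-meal food effect.
- **That dividing by Day 1 AUC(0-inf) simply repairs the analysis.** It is least derivable where carry-over is largest. Protocol 10.4.1 names AUC(0-inf) for Part B only among dose-normalised parameters, as data permit.

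**Conclusion.** The label is wrong as written. Under once-daily dosing, Day 3 AUC(0-24) over Day 1 AUC(0-24) is an accumulation ratio and equals relative bioavailability only when carry-over is nil. That conclusion needs no assumption about release.

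The size does need one. With unchanged bioavailability, linear one-compartment kinetics and the protocol's half-life range, the ratio could read anywhere from essentially 100% to well above 120%. The documents do not say which case applies, and they do not show that any decision would be altered. This is a minor-to-moderate point of labelling and interpretation in a secondary analysis.

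**What to change.** In SAP 8.2.5.2, SAP 10.6.4.1, Table 3.12 and Figure 3.13, name the Day 3/Day 1 ratios of AUC(0-24) and Cmax accumulation ratios. Remove the day comparison from the Frel list, and state that these ratios are not to be interpreted as a change in absorption. Defining MT-12h in SAP 5.1 would let readers judge how much carry-over to expect. The model, data and 90% intervals stay as they are, so the cost is wording.

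Optionally, add Day 3 AUC(0-24) over Day 1 AUC(0-inf) as a repeat-dose relative bioavailability. Report it only for participants whose Day 1 terminal slope can be estimated from the 24 h of sampling, and show AUC%extrap beside it. That parameter is on neither document's Part B list and would have to be added. The drawback is that this ratio will often not be derivable when release continues to 24 h, so the renaming should not depend on it.

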## 10.7. Appendix 7: Reporting Standards for Missing Data

### 10.7.1. Premature Withdrawals

Element	Reporting Detail
General	
 
Subject study completion (i.e. as specified in the protocol) was defined as one who completes all phases of the study including the last scheduled procedure shown in the SoA i.e. the follow-up visit.
 
Withdrawn subjects may be replaced in the study.
 
All available data from participants who were withdrawn from the study will be listed and all available planned data will be included in summary tables and figures, unless otherwise specified.
 

### 10.7.2. Handling of Missing Data

Element	Reporting Detail
General	
 
Missing data occurs when any requested data is not provided, leading to blank fields on the collection instrument: 
 
These data will be indicated by the use of a "blank" in subject listing displays. Unless all data for a specific visit are missing in which case the data is excluded from the table.
 
Answers such as "Not applicable" and "Not evaluable" are not considered to be missing data and should be displayed as such.
 
 
 

Outliers	
 
Any participants excluded from the summaries and/or statistical analyses will be documented along with the reason for exclusion in the clinical study report.
 

#### 10.7.2.1. Handling of Missing and Partial Dates

Element	Reporting Detail
General	
 
Partial dates will be displayed as captured in subject listing displays.
 

Adverse Events	
 
The eCRF allows for the possibility of partial dates (i.e., only month and year) to be recorded for AE start and end dates; that is, the day of the month may be missing. In such a case, the following conventions will be applied for calculating the time to onset and the duration of the event: 
 
Missing Start Day: First of the month will be used unless this is before the start date of study treatment; in this case the study treatment start date will be used and hence the event is considered On-treatment as per Appendix 4: Study Phases and Treatment Emergent Adverse Events.
 
Missing Stop Day: Last day of the month will be used, unless this is after the stop date of study treatment; in this case the study treatment stop date will be used.
 
 
 
Completely missing start or end dates will remain missing, with no imputation applied. Consequently, time to onset and duration of such events will be missing.
 

Concomitant Medications/ Medical History	
 
Partial dates for any concomitant medications recorded in the CRF will be imputed using the following convention: 
 
If the partial date is a start date, a '01' will be used for the day and 'Jan' will be used for the month
 
If the partial date is a stop date, a '28/29/30/31' will be used for the day (dependent on the month and year) and 'Dec' will be used for the month.
 
 
 
The recorded partial date will be displayed in listings.
 

## 10.8. Appendix 8: Values of Potential Clinical Importance

### 10.8.1. Laboratory Values

Haematology				
Laboratory Parameter	Units	Category	Clinical Concern Range	
			Low Flag (< x)	High Flag (>x)
Hematocrit	Ratio of 1	Male		0.54
		Female		0.54
		Δ from BL	↓0.075	
Hemoglobin	g/L	Male		180
		Female		180
		Δ from BL	↓25	
Lymphocytes	x10  / L		0.8	
Neutrophil Count	x10  / L		1.5	
Platelet Count	x10  / L		100	550
White Blood Cell Count (WBC)	x10  / L		3	20

Clinical Chemistry				
Laboratory Parameter	Units	Category	Clinical Concern Range	
			Low Flag (< x)	High Flag (>x)
Albumin	G/L		30	
Calcium	mmol/L		2	2.75
Creatinine	umol/L			1.3 X ULN
Creatinine	umol/L	Δ from BL		↑ 44.2
Glucose	mmol/L		3	9
Potassium	mmol/L		3	5.5
Sodium	mmol/L		130	150
Total CO 2	mmol/L		18	32

Liver Function				
Test Analyte	Units	Category	Clinical Concern Range	
ALT/SGPT	U/L	High	≥ 2x ULN	
AST/SGOT	U/L	High	≥ 2x ULN	
AlkPhos	U/L	High	≥ 2x ULN	
T Bilirubin	μmol/L	High	≥ 1.5x ULN	
T. Bilirubin + ALT	μmol/L U/L	High	1.5xULN T. Bilirubin + ≥ 2x ULN ALT	

### 10.8.2. ECG

ECG Parameter	Units	Clinical Concern Range	
		Lower	Upper
Absolute			
Absolute QTc Interval	msec	≤ 450	
		> 450	<480
		≥ 480	<500
		≥ 500	
Absolute PR Interval	msec	< 110	> 220
Absolute QRS Interval	msec	< 75	> 110
Change from Baseline			
Increase from Baseline QTc	msec	≤ 30	
	msec	> 30	<60f
	msec	≥ 60	

### 10.8.3. Vital Signs

Vital Sign Parameter (Absolute)	Units	Clinical Concern Range	
		Lower	Upper
Systolic Blood Pressure	mmHg	< 85	> 160
Diastolic Blood Pressure	mmHg	< 45	> 100
Heart Rate	bpm	< 40	> 110

Vital Sign Parameter (Change from Baseline)	Units	Clinical Concern Range			
		Decrease		Increase	
		Lower	Upper	Lower	Upper
Systolic Blood Pressure	mmHg	≥ 20	≥ 40	≥ 20	≥ 40
Diastolic Blood Pressure	mmHg	≥ 10	≥ 20	≥ 10	≥ 20
Heart Rate	bpm	≥ 15	≥ 30	≥ 15	≥ 30

**10.9. Appendix 9: Pharmacokinetic Analyses**

**10.9.1. Systems**

N/A

## 10.10. Appendix 10: Abbreviations & Trade Marks

### 10.10.1. Abbreviations

Abbreviation	Description
AE	Adverse Event
AIC	Akaike's Information Criteria
A&R	Analysis and Reporting
CDISC	Clinical Data Interchange Standards Consortium
CI	Confidence Interval
CPMS	Clinical Pharmacology Modelling & Simulation
CS	Clinical Statistics
CSR	Clinical Study Report
CTR	Clinical Trial Register
DBF	Database Freeze
DBR	Database Release
DOB	Date of Birth
DP	Decimal Places
eCRF	Electronic Case Record Form
FDA	Food and Drug Administration
FDAAA	Food and Drug Administration Clinical Results Disclosure Requirements
GCSP	Global Clinical Safety and Pharmacovigilance
GSK	GlaxoSmithKline
IA	Interim Analysis
ICH	International Conference on Harmonization
IDSL	Integrated Data Standards Library
MMRM	Mixed Model Repeated Measures
PCI	Potential Clinical Importance
PD	Pharmacodynamic
PDMP	Protocol Deviation Management Plan
PK	Pharmacokinetic
PP	Per Protocol
PopPK	Population PK
QC	Quality Control
QTcF	Friderica's QT Interval Corrected for Heart Rate
QTcB	Bazett's QT Interval Corrected for Heart Rate
RAP	Reporting & Analysis Plan
RAMOS	Randomization & Medication Ordering System
SAC	Statistical Analysis Complete
SDSP	Study Data Standardization Plan
SDTM	Study Data Tabulation Model
SOP	Standard Operation Procedure
TA	Therapeutic Area
TFL	Tables, Figures & Listings

**10.10.2. Trademarks**

Trademarks of the GlaxoSmithKline Group of Companies
None

Trademarks not owned by the GlaxoSmithKline Group of Companies
SAS
WinNonlin

## 10.11. Appendix 11: List of Data Displays

### 10.11.1. Data Display Numbering

The following numbering will be applied for RAP generated displays:

Section	Tables	Figures
Study Population	1.1 to 1.n	1.1 to 1.n
Safety	2.1 to 2.n	2.1 to 2.n
Pharmacokinetic	3.1 to 3.n	3.1 to 3.n
Section	Listings	
ICH Listings	1 to x	
Other Listings	y to z	

